3.2 Morbidity Trial

Assuming approximately 12% baseline resistance (based on previous studies) and an ICC of approximately 0.051 (derived from the TEF study), we anticipate approximately 80% power to detect a difference of 18% (i.e., comparing 12% to 30%) assuming 80% carriage of pneumococcus and 10 specimens per community. For resistome comparisons, we anticipate approximately 80% power to detect a 16% difference (comparing 12% to 28%). We anticipate five such comparisons: (1) nasopharyngeal DNA, (2) nasopharyngeal RNA, (3) rectal DNA sequencing, (4) rectal RNA sequencing, and (5) rectal TAC-card.

4 Randomization

Simple random sampling will be used in each country. Within each country, a full list of eligible communities will be provided, and used to fill a column of a table. A second column will be populated with treatment arm names as follows. First, fifteen rows will be filled with the name **AzithroPlus**, and fifteen with the name **ControlPlus**. Then, one half of the remaining rows (rounding to even) will be filled with the name **Azithro**, and the remaining filled with the name **Control**. This column will be shuffled at random, yielding an assignment for each community.

Note that there is no stratification other than country, and the morbidity communities are randomized from the same pool as the mortality communities.

The randomization will be conducted using R. The function sample with option replace=FALSE will be used to conduct the random shuffling. Note that the choice of the random number seed completely determines the randomization. To ensure the integrity of the randomization, we will choose the seed as follows. We will use the units (least significant digit) of the daily high Fahrenheit temperature in eleven selected US cities on 15 July 2013 as reported by the National Weather Service. A confidential ordered list of these cities will be provided to the DSMC.

Masking will be strictly enforced. Each study site will provide one individual to whom the randomization list will be provided. Investigators and field teams must remain masked and must make no effort to determine which arm a community has been randomized to within the mortality trial or within the morbidity trial.

5 Abbreviations

ANCOVA Analysis of covariance

DSMC Data and Safety Monitoring Committee

HAZ height for age Z score

MUAC Mid upper arm circumference

SAP Statistical Analysis Plan

TF Trachomatous inflammation—follicular

TI Trachomatous inflammation-intense

WAZ weight for age Z score

WHZ weight for height Z score

6 Revisions History

- 1. **3 March 2016.** Clarified the planned interim analysis for efficacy.
- 2. 26 April 2016. Clarification of timing of verbal autopsy collection.
- 3. **28 June 2016.** Clarification of original power calculations, plus supplementary assessment now that trial is underway.
- 4. 1 Feb 2017. Clarified and added secondary analyses for Mortality (page 5).
- 5. 1 Feb 2017. Added secondary analyses for Morbidity (page 6).
- 6. **1 Feb 2017.** Added statistical information for the microbiome analyses for Morbidity (page 7).
- 7. 6 April 2017. Page 5, Section 2.1.1. Added the secondary analysis after the DSMC meeting due to the fact that some persons may not be captured at all censuses, but still be alive or dead at the end of phase24. :

A secondary analysis will be conducted by doing the following. Data will be formatted to include the Phase 24 vital status of all persons found alive at any of the Phases 0, 6, and 12 (with no indication of them dying in the interim) instead of only considering the vital status of persons alive at phase 18 census

8. **24 May 2017 Page 7, Section 2.1.3 Microbiome** Added the primary analysis for the 12-month MB samples.

Primary Analyses for the 12 month rectal swabs will conducted on pooled samples. Samples will be pooled in the lab by combining equal aliquots of 10 individual's rectal swabs into one microbiome sample per village. There will be one pooled sample of 10 specimens for each of the 30 villages, giving us 30 samples total. We will test for Alpha diversity of the sample (or Gamma diversity of the village) comparing the two arms using a permutation test and not correcting for baseline (post test only).

9. 5 June 2017 Page 7, Section 2.1.3 Microbiome (revised).

Primary Analyses for the 12 month rectal swabs will conducted on pooled samples. Samples will be pooled in the lab by combining aliquots of equal nucleic acid content by QuBit measurement of 10 individual's rectal swabs into one microbiome sample per village. There will be one pooled sample of 10 specimens for each of the 30 villages, giving us 30 samples total. We will use PERMANOVA on an L1-norm distance on bacterial OTUs (which have undergone rarefication) to determine if treatment significantly explains the difference between the two groups.

Secondary Analysis will include:

- L2-norm distance PERMANOVA on bacterial OTUs
- virus, parasites, fungi, etc
- Simpson's and Shannon's estimated gamma diversities (transformed into effective number) will be compared by arm using a permutation test without correcting for baseline (ie post test only).

10. 10 June 2017 Page 7, Section 2.1.3 Microbiome (revised).

Analysis for rectal swabs, RNA-sequencing

Primary Analyses for the 12 month rectal swabs will conducted on pooled samples. Samples will be pooled in the lab by combining aliquots of equal nucleic acid content by QuBit measurement of 10 individual's rectal swabs into one microbiome sample per village. There will be one pooled sample of 10 specimens for each of the 30 villages, giving us 30 samples total for the RNA-seq processing. We will use PERMANOVA on an L2-norm distance on bacterial reads to determine if treatment significantly explains the difference between the two groups.

Secondary Analysis will include:

- L1-norm distance PERMANOVA on bacterial reads
- virus, parasites, fungi, etc
- Simpson's and Shannon's estimated gamma diversities (transformed into effective number) will be compared by arm using a permutation test without correcting for baseline (ie post test only).

Analysis for conjunctiva swabs, RNA-sequencing

Primary Analyses for the 12 month conjunctiva swabs-RNA sequencing will conducted on pooled samples. Samples will be pooled in the lab by combining aliquots of equal nucleic acid content by QuBit measurement of 10 individual's conjunctival swabs into one microbiome sample per village. There will be one pooled sample of 10 specimens for each of the 30 villages, giving us 30 samples total for RNA sequencing. We will use PERMANOVA on an L2-norm distance on bacterial reads to determine if treatment significantly explains the difference between the two groups.

Secondary Analysis will include:

• L1-norm distance PERMANOVA on bacterial reads

- virus, parasites, fungi, etc
- Simpson's and Shannon's estimated gamma diversities (transformed into effective number) will be compared by arm using a permutation test without correcting for baseline (ie post test only).

Analysis for conjunctiva swabs, 16S-sequencing

Primary Analyses for the 12 month conjunctiva swabs-16 sequencing will be conducted on individual samples. We will use PERMANOVA on an L1-norm distance on bacterial OTUs to determine if treatment significantly explains the difference between the two groups.

Secondary Analysis will include:

- L2-norm distance PERMANOVA on bacterial OTUs
- Simpson's and Shannon's estimated gamma diversities (transformed into effective number) will be compared by arm using a permutation test without correcting for baseline (ie post test only).

11. 29 June 2017 Pages: 4-6 Secondary Analysis for Mortality study were numerated, and clarified. Secondary Analysis for Morbidity study were also numerated, and clarified. Microbiome Section was divided into 4 sections and modified.

12. 3 March 2018 Page 6: Secondary analysis item 15 added per BMGF request (subgroups among malnutrition).

13. 11 June 2018. Sample size calculations from original BMFG proposal updated and transferred to SAP, page 7. The exact analyses for the Niger study have been clarified.

14. 21 August 2018. Additional unplanned secondary analyses for geography and dose added; reporting for per-protocol analysis clarified.

15. 22 April 2019. Page 9, Section 2.1.3 Microbiome (revised).

Primary analysis for rectal swabs at 36-months, DNA-sequencing

Primary analysis on the rectal swabs will be conducted on pooled samples. We will be using DESeq2 to determine if Campylobacter upsaliensis is upregulated in the placebo arm compared to the azithromycin arm. LEfSe will be used as a sensitivity test.

Secondary analysis for rectal swabs at 36-months

We propose to compare the normalized abundance of MLS reads between treatment arms. Resistance to other classes of antibiotics will be compared. In addition, we will also assess for a difference in the normalized abundance of betalactams reads. P-values will NOT be corrected for multiple comparisons.

Changed conjunctival samples sequencing from 12 months to 24 moths.

16. 15 July 2019. Page 9, Section 2.1.3.5 Secondary MicrobiomeAnalysis (revised).

Secondary analysis for rectal swabs at 36-months

We propose to compare the normalized abundance of MLS reads between treatment arms. Resistance to other classes of antibiotics will be compared. In addition, we will also assess for a difference in the normalized abundance of betalactams reads. P-values will NOT be corrected for multiple comparisons. Instead, we will estimate the FDR for resistance to each class of antibiotic. Mortality Reduction after Oral Azithromycin

Contingency Study, Niger, Years 3-4

Statistical Analysis Plan

UCSF Francis I. Proctor Foundation

The Carter Center

Niger Ministry of Health

Johns Hopkins University Dana Center and Bloomberg School of Public Health

Tanzania National Institute for Medical Research and Muhumbili Medical Center

London School of Hygiene and Tropical Medicine

University of Malawi, Blantyre College of Medicine

Malawi Ministry of Health

Introduction

This document (Statistical Analysis Plan, SAP) describes the planned analysis and reporting for the clinical trial, **Mortality Reduction after Oral Azithromycin**, Contingency Study, Years 3-4, Niger. It includes specifications for the statistical analyses and tables to be prepared for the interim and final Clinical Study Report. This study is a Phase IV clinical trial to compare methods to reduce childhood mortality using mass administration of azithromycin (Pfizer, CAS 83905-01-5) compared to placebo. The content of this Statistical Analysis Plan meets the requirements stated by the US Food and Drug Administration and conforms to the American Statistical Association's Ethical Guidelines.

The following documents were reviewed in preparation of this Statistical Analysis Plan:

- Mortality Reduction after Oral Azithromycin, Protocol
- Mortality Reduction after Oral Azithromycin, Statistical Analysis Plan
- Mortality Reduction after Oral Azithromycin, Manual of Operations
- ICH Guidance on Statistical Principles for Clinical Trials

The planned analyses described in this SAP will be included in future manuscripts. Exploratory analyses not necessarily identified in this Statistical Analysis Plan may be performed to support the analysis. Unplanned analyses not delineated in this Statistical Analysis Plan will be documented as such in the final Clinical Study Report and manuscripts.

This document will be reviewed prior to the enrollment of patients. All subsequent changes will be indicated by detailed change log in the Appendix.

MORDOR Stage 2 Contingency Study

1 Introduction

Should the primary analysis of azithromycin to prevent mortality reveal evidence of a benefit, we propose to proceed with two additional studies in Stage 2.

2 Design

Contingency study A. All communities in Niger will receive treatment at the conclusion of MORDOR Stage 1 (original study). Specifically, azithromycin communities will continue with azithromycin, and placebo communities will receive azithromycin at the 24 month visit (census number 5). Follow-up will occur at month 30 and month 36, providing one additional year of data.

Contingency study B. At the 36 month visit, rerandomization will occur, and half of communities will begin to receive placebo.

3 Analysis

The primary outcome is mortality, analyzed in the same way as in MORDOR Stage I, i.e., present on an initial census, and absent on the next follow-up census due to death.

Study A:

- 1. Sample size considerations.
 - a. Assuming communities of size 668 with approximately 17% in the target age range, an effect size of 20%, 10% loss to follow-up per year, 2% mortality per year, and a CV of 0.51, 312 communities per arm provides approximately 87% power (see MORDOR Phase I SAP for details).
 - b. Updating based on data from Phase I (Niger), we find the following. Assuming the observed CV of 0.34, a death rate of 2% per year results in approximately 80% power to detect a 17% effect. A death rate of 2.5% per year (and a CV of 0.34) result in approximately 80% power to detect a 15.5% effect size.
- 2. Primary prespecified analysis: We propose to compare the former placebo arms with the former azithromycin arms, using negative binomial regression. Significance testing is two-sided with an alpha of 0.05, and will be based on permutation testing. (This analysis is identical in every way to the country subgroup analyses conducted in Stage 1). This is restricted to the period from 24 months to 36 months, covering two six-month study intervals.
- 3. We propose, as a prespecified secondary analysis, a longitudinal comparison of the original placebo communities. We propose to contrast the first four study intervals during which these communities received placebo, to the last two study intervals

during which these communities received azithromycin. Analysis will be conducted using negative binomial regression, with a permutation P-value reported (two-sided, alpha=0.05). The community-randomized nature of the trial is thus taken into account.

- 4. Additional supplementary analyses will be distinguished from the two prespecified analyses above. In particular, the following will be reported:
 - a. Analysis of the seasonality and timing of deaths: time of death, time of treatment for those who died, and time since treatment for all deaths. We will conduct comparisons of time since treatment conditional on death based on the Cramer-von Mises test (exactly as in Stage 1), additionally comparing across treatment arms and longitudinally. Comparisons of equality of circular means will be used to assess seasonality of death and of treatment, comparing between randomization arms and longitudinally. We will, in particular, focus special attention and reporting to a comparison of phases 1-4 to 5-6 within the placebo arm.
 - b. Analysis will be reported according to the same age classes used in the original study (Keenan et al, NEJM, 2018), i.e. 1-5, 6-11, 12-23, 24-59 months.
 - c. We will examine the difference between phase 5 and 6 in the same way.
 - d. We will report longitudinal analysis of mortality changes in the original azithromycin arm, using a linear predictor of study interval (1-6).
 - e. We will compare estimated treatment effect at a regional level using placebo mortality rates as a predictor.

Study B (year two of mortality contingency study)

- 1. Sample size considerations are the same as in Study A (year 1).
 - a. Assuming communities of size 668 with approximately 17% in the target age range, an effect size of 20%, 10% loss to follow-up per year, 2% mortality per year, and a CV of 0.51, 312 communities per arm provides approximately 87% power (see MORDOR Phase I SAP for details).
 - b. Updating based on data from Phase I (Niger), we find the following. Assuming the observed CV of 0.34, a death rate of 2% per year results in approximately 80% power to detect a 17% effect. A death rate of 2.5% per year (and a CV of 0.34) result in approximately 80% power to detect a 15.5% effect size.
- 2. The primary prespecified analysis will contrast the rerandomized placebo arm with the rerandomized azithromycin arm. This will be conducted with negative binomial regression, using a two-sided alpha of 0.05 and a permutation test by randomization arm.
- 3. Supplementary analyses will control for prior history (original randomization arm).
- 4. Longitudinal analysis for communities who always received azithromycin will be reported.
- 5. We will compare all four groups for the last year of data (two histories by two final treatments).
- 6. Additional analyses by the same age groups as before and by phase will be reported.
- 7. Models of timing, seasonality, and geography will be reported as secondary analysis.

Morbidity Study. Analysis of morbidity communities will follow the exact template as Stage I. Primary prespecified analyses will be two-sided, at an alpha of 0.05. However, the morbidity communities are still receiving placebo. Note that we will report the full follow-up at 48 months separately from the Stage 1 primary analyses. We will also look for secular effects longitudinally over the four years of the full study, as well as phases 5-8 separately.

- 1. Anthropometry: we will examine height and weight longitudinally, and WFH Z score secondarily. Please see the Stage 1 SAP for details.
- 2. Other analyses will include drug resistance and malaria, as in Stage 1.
- 3. Note that we do not do nares or conjunctiva swabs, conjunctival photos, or any swabs on 7-12 year olds in the contingency study.

Statistical considerations

- 1. Communities which drop out of the study will be omitted from analysis for all study period for which we have no data for that community. If a community rejoins at a particular phase, it will be included as before.
- 2. Evidence of poor model fit to the negative binomial regression will justify reporting additional models.
- 3. Permutation tests will be conducted with 10000 replications. If the critical value 0.05 lies within the Monte Carlo confidence interval for the P-value, we will replicate with 10,000,000 replications, and this will be reported.

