1.2 Morbidity Trial

The trial profile is given in the Manual of Operations. In the morbidity trials, communities are randomized to two arms: **AzithroPlus**, or **ControlPlus**. At each study site, 15 communities each are randomized to **AzithroPlus** and to **ControlPlus**. The trial is a placebo controlled, double masked, community randomized, multicenter clinical trial. The profile is given in the Manual of Operations, Ch. 3.

2 Statistical Analysis

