2.1.2 Morbidity Trials

Primary Analyses (Morbidity Study).

The morbidity analyses are to be conducted on a country-specific basis. Each outcome will be addressed in a separate analysis. Outcomes are taken at 0, 12, and 24 months.

The outcome and analysis plan for all non-core studies must be submitted to the Steering Committee for approval.

The outcomes for this study are listed on www.clinicaltrials.gov. Analyses may be conducted at the village level (accounting thus for clustering), or, when possible, at the individual level accounting for clustering by using mixed effects regression. The listed primary outcomes (4 February 2015) are:

- 1. Height over time in children aged 1-60 months (Niger & Malawi)
- 2. Weight, corrected for height over time in children aged 1-60 months (Niger & Malawi)
- 3. Fraction of macrolide resistance in nasopharyngeal swabs in children 1-60 months (core). Note that for Niger, this is phenotypic, and is a binary outcome at the individual level.
- 4. Fraction of macrolide resistance from stool specimens in children 1-60 months (core). For Niger, this includes RNA, DNA, and TAC-card methods (a binary outcome at the individual level).
- 5. Fraction of macrolide resistance by nasal swabs in children 1-60 months (Niger only). For Niger, this is based on RNA and DNA sequencing (a binary outcome at the individual level).
- 6. Presence of malaria parasites in children 1-60 months (core activity)
- 7. Fraction of conjunctival swabs yielding ocular chlamydia in children 1-60 months (Niger)

Nonnormality, heteroskedasticity, clustering, and outliers will be assessed appropriately.

Secondary Analyses (Morbiditiy Study).

Common templates will be used. Analysis will use cluster-level variables for malaria parasites, macrolide resistance in NP swabs, macrolide resistance in nasal swabs, macrolide resistance in stool specimens, and ocular chlamydia. Clustered logistic regression using baseline values will be used, with the outcome being the 12 and 24 month observations, and time and treatment as covariates in addition to baseline values. Permutation P-values will be reported.

Model checking will be performed to identify poorly fitting models, using the residuals versus fitted values plot and by finding high leverage points. Significance testing will be conducted using permutation tests.

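### For Niger, the single primary outcome of stool macrolide resistance has three binary laboratory readouts, and the SAP names neither a deciding method nor an adjustment

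*SAP*

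**What the plan says.** SAP 2.1.2 says that the morbidity analyses are run country by country, with a separate analysis for each outcome. Item 4 of its primary outcomes is macrolide resistance in stool from children aged 1-60 months, a core outcome. For Niger it adds: "For Niger, this includes RNA, DNA, and TAC-card methods (a binary outcome at the individual level"). No such list of methods is given for Malawi or Tanzania.

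Item 3 is resistance in nasopharyngeal swabs, with the remark: "Note that for Niger, this is phenotypic, and is a binary outcome at the individual level". Item 5 is resistance in nasal swabs, Niger only, based on RNA and DNA sequencing.

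SAP 3.2 gives two power statements. For cultured pneumococcus, "we anticipate approximately 80% power to detect a difference of 18% (i.e., comparing 12% to 30"%). For what it calls resistome comparisons, "we anticipate approximately 80% power to detect a 16% difference (comparing 12% to 28"%). It then adds: "We anticipate five such comparisons: (1) nasopharyngeal DNA, (2) nasopharyngeal RNA, (3) rectal DNA sequencing, (4) rectal RNA sequencing, and (5) rectal TAC-card".

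Section 3.2 states no significance level. The morbidity paragraph of the Niger contingency SAP, which says that it follows the Stage I template, uses two-sided 0.05.

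The SAP does address multiplicity elsewhere. In 2.1.2 it adjusts p-values for the secondary z-score and MUAC outcomes. In 2.1.3.5 it declines to correct the 36-month resistance-class comparisons but will estimate a false discovery rate. Neither provision reaches item 4.

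**The concern.** A primary outcome should give one answer. Here one listed outcome yields three binary results, and 3.2 confirms that they are three comparisons rather than components of a composite. Gene presence, gene expression and a targeted card can disagree. If one of the three shows a difference and two do not, the plan does not say whether stool resistance increased.

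Emergent macrolide resistance is Objective 4 of the protocol, and the executive summary says that it could limit adoption of mass treatment. An open choice of readout can mislead either way: a chance finding on one method may be reported as emerging resistance, or a reassuring method may be put forward when another shows an effect. It also sits badly with the principle in 2.1.2 that the model be fully prespecified before any analysis.

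A second question follows from 3.2. The stated power is per comparison, and the section does not say which of the five comparisons are primary. A reader cannot tell what the 80% supports.

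**Working it through.** **Inputs.** From SAP 3.2: "Assuming approximately 12% baseline resistance (based on previous studies) and an ICC of approximately 0.051 (derived from the TEF study"); resistance of 12% v 28%; "assuming 80% carriage of pneumococcus and 10 specimens per community". From SAP 1.2, at each site "15 communities each are randomized to" each arm. Assumptions: all 10 specimens count for a resistome comparison (the carriage figure applies to culture), and testing is two-sided.

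**1. Reproducing the stated 80%.**
- Design effect: 1 + (10 − 1) × 0.051 = 1.459.
- Effective number per arm: 15 × 10 / 1.459 = 102.8.
- Variance of the difference: (0.12 × 0.88 + 0.28 × 0.72) / 102.8 = 0.3072 / 102.8 = 0.00299, so the standard error is 0.0547.
- Standardised difference: 0.16 / 0.0547 = 2.93.
- Power at two-sided 0.05, normal formula: Φ(2.93 − 1.96) = 83.3%. With 14 clusters per arm, to mirror the extra cluster in the formula in SAP 3.1, it is 80.7%.
- Cluster-level t test on 28 degrees of freedom: 80.7%. Hayes-Moulton form: 79.4%. Beta-binomial simulation, 20,000 runs: 80.5%.

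A continuity-corrected formula gives 77.3%, and one-sided 0.05 gives 89.4%. The stated figure is therefore what one obtains for a single comparison at unadjusted two-sided 0.05.

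**2. False-positive chance for the one stool outcome.** With three tests at 0.05 each:
- Independent: 1 − 0.95³ = 14.3%.
- Equal correlation r between the test statistics: 1 − ∫ φ(u) [Φ((1.96 − √r·u)/√(1 − r)) − Φ((−1.96 − √r·u)/√(1 − r))]³ du. This gives 12.5% at r = 0.5 and 9.8% at r = 0.8.

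The documents give no correlation, so 0.5 and 0.8 are assumptions. The tests use specimens from the same communities, so independence is best read as an upper figure.

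**3. Power if the three stool methods were co-primary.** Bonferroni gives 0.05 / 3 = 0.0167, with a normal critical value of 2.39.
- Normal formula: Φ(2.93 − 2.39) = 70.3%; with 14 clusters, 66.8%.
- t test, 28 degrees of freedom: 64.9%. Hayes-Moulton: 65.0%. Simulation: 65.1%.

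So power is about 65% to 70% at 10 specimens per community. Protocol 5.2.1 samples 40 children per community. If all 40 were processed individually (design effect 1 + 39 × 0.051 = 2.989), power at 0.0167 would be about 93% to 96%.

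**4. The five comparisons set against the listed Niger primaries.**

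| SAP 3.2 comparison | SAP 2.1.2 primary outcome, Niger |
|---|---|
| Nasopharyngeal DNA | No match: item 3 is phenotypic |
| Nasopharyngeal RNA | No match: item 3 is phenotypic |
| Rectal DNA sequencing | Item 4 |
| Rectal RNA sequencing | Item 4 |
| Rectal TAC-card | Item 4 |
| (none) | Item 5: nasal swabs by RNA and DNA sequencing |

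Three of the five belong to the stool outcome. The two nasopharyngeal entries match no listed primary, and the sequencing that 2.1.2 does list, on nasal swabs, is not among the five.

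**The case against.** The strongest reply is that the SAP's power figure is not wrong. It reproduces as a per-comparison figure, and 3.2 never claims it for a jointly controlled set. That stands. A reader might infer that 80% is an error and that the true figure is nearer 60%, the result of a Bonferroni level of 0.01 over all five. The documents do not support this. They do not call all five comparisons primary, two of the five match no listed primary, and nothing in the plan requires family-wise control across them.

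It can also be said that adjustment is unwise for a harm, because it makes the trial less sensitive to resistance. This has force, and it is why naming a single method is better than dividing the significance level. It does not excuse leaving the readout open, since that also permits selective reassurance.

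The separate-analysis rule in 2.1.2 might be read as deliberate acceptance of unadjusted tests. It covers different outcomes, however, not three methods for the same outcome. Reading the three as a composite is contradicted by 3.2. SAP 2.1.3.5 does make rectal TAC-card analysis secondary, but that entry compares bacteria and viruses between arms, not the binary resistance outcome. Protocol 9.3 and 13.3 describe culture and PCR gene detection and do not settle the choice.

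Two limits remain. The three-method definition applies to Niger only. And 2.1.2 refers to the trial registry for the outcome list, which was not available here; it may name a readout, although the SAP should then repeat it.

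**Conclusion.** The point holds for Niger. One primary outcome has three binary readouts that the SAP itself counts as separate comparisons, with no deciding method, combination rule or adjustment. At two-sided 0.05 each, the chance of at least one false positive for this outcome is about 14% if independent and about 10% to 13% at assumed correlations of 0.8 to 0.5. The 0.05 level is inferred from the contingency SAP and from reproducing the 80%.

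The power statement is correct as far as it goes. What is missing is a sentence saying that it is per comparison. The figure of 65% to 70% arises only if all three stool methods are kept as co-primary under Bonferroni at 10 specimens per community. The mismatch between the nasopharyngeal entries in 3.2 and items 3 and 5 of 2.1.2 is real and needs reconciling whatever view is taken of multiplicity.

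**What to change.** 1. In SAP 2.1.2 item 4, before any unmasked analysis, name one method as the primary stool readout for Niger and label the other two secondary. Alternatively, keep all three and apply Holm across them. If stool results by arm are already known when the choice is made, report that.
2. In SAP 3.2, state that the power of about 80% for 12% v 28% is per comparison, at two-sided 0.05, with 10 specimens per community, and so applies to the single named method. If all three are kept as co-primary, add that power is about 65% to 70% at 0.0167 (Bonferroni, 10 specimens).
3. In SAP 3.2, mark which of the five resistome comparisons are primary and which secondary, and reconcile nasopharyngeal DNA and RNA with items 3 and 5 of 2.1.2.

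The cost is a few sentences. Naming one method leaves the sample size and the stated power unchanged; the price is committing to a method in advance. Keeping three costs roughly 10 to 15 points of power per comparison under Bonferroni at 10 specimens (from 79-83% to 65-70%). Holm is never less powerful than Bonferroni.

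### Study A item 3 compares the former placebo communities before and after a switch they all make at month 24, so its P-value cannot separate drug effect from calendar change

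*SAP*

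**What the plan says.** All references are to the Contingency Study SAP (Niger, Years 3-4) unless stated.

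- **Section 2, Design, Study A.** Communities originally on azithromycin stay on it. All original placebo communities move to azithromycin at the 24-month visit, with follow-up at months 30 and 36.
- **Section 3, Study A item 2 (primary).** The two original arms are compared over months 24-36, when both are on azithromycin.
- **Section 3, Study A item 3 (prespecified secondary).** Within the original placebo communities only, "We propose to contrast the first four study intervals during which these communities received placebo, to the last two study intervals", the latter on azithromycin. The method is negative binomial regression with a permutation P-value, two-sided, alpha 0.05. The item ends: "The community-randomized nature of the trial is thus taken into account". It does not say which labels are permuted, and it names no concurrent arm, calendar term or interaction.
- **Study A item 4.** "Additional supplementary analyses will be distinguished from the two prespecified analyses above", so item 3 is one of the two. Item 4a returns to the same contrast for timing of deaths and will "focus special attention and reporting to a comparison of phases 1-4 to 5-6 within the placebo arm". Item 4d separately fits a linear slope over intervals 1-6 in the original azithromycin arm.

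**The concern.** Within one arm that switches all at once, period and treatment are the same variable. A fall in deaths after month 24 may be the drug, a better year, or a continuing decline, and nothing inside item 3 can tell these apart.

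Permutation does not help. The trial randomized arm, and item 3 keeps only one arm. The labels left to permute are periods, which were not randomized, so the test is of no change over time rather than no drug effect. The closing sentence of item 3 is right if it means clustering. A reader could take it to mean that randomization protects the contrast, which it does not.

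Whole years on each side (two before, one after) roughly balance a regular season but not year-to-year change, and the after period is a single year. Protocol Chapter 2 describes recent progress in under-5 mortality. That statement is general, gives no rate and is not specific to Niger, but its direction is the one that would mimic a benefit.

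Item 3 matters because it is the only one of Study A's two prespecified analyses that sets placebo against azithromycin. Read as a drug effect, a significant result could be produced by background decline, and a background rise could hide a real benefit.

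**Working it through.** **1. The plan's own figure.** The SAP states no power for item 3. For the Study A between-arm comparison it states about 87% (312 communities per arm, 668 people, 17% in age range, 20% effect, 10% loss, 2% mortality, CV 0.51). With the formula in SAP 3.1:

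- y = 668 x 0.17 x 0.90 = 102.2 person-years per community
- numerator = (0.020 + 0.016)/102.2 + 0.51^2 x (0.020^2 + 0.016^2) = 0.000523
- z = sqrt(311 x 0.004^2 / 0.000523) - 1.96 = 1.125, so power = 87.0%

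The updated figures also come close: 81.9% and 81.3%, against a stated 80% for each.

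**2. Inputs for item 3.** From SAP 3.1.2 (June 2016 assessment for size and number): 622/2 = 311 communities per arm, 688 people, 16.7% in age range, death rate r = 0.020 or 0.025 per year, loss of 0 or 10% per year (factor f = 1 or 0.95, half-interval credit). Assumed here: an extra within-community, between-period CV kw of 0 or 0.34. Persistent differences between communities drop out of a before-after contrast.

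**3. Formula.** Person-years per year PY = 311 x 688 x 0.167 x f = 35,733 or 33,946. Deaths are D1 = 2 x PY x r and D2 = PY x r x m, where m multiplies the period-2 rate. SE of the log ratio = sqrt(1/D1 + 1/D2 + 2kw^2/311). Rejection is the two-sided normal probability at log(m). With no change, D1 = 1,358-1,787 and D2 = 679-893.

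Worked case (f = 1, r = 0.025, kw = 0, 5% fall): D1 = 1,787, D2 = 849, SE = 0.0417, log(0.95)/SE = -1.23, rejection 23%.

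**4. Results for item 3.** The period midpoints are 18 months apart, so total falls of 3%, 5% and 10% are 2.0%, 3.4% and 6.8% per year, e.g. 1 - 0.95^(1/1.5) = 3.4%.

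| Drug effect | Background change (assumed, total) | P<0.05 |
|---|---|---|
| none | 3% fall | 9-11% |
| none | 5% fall | 15-23% |
| none | 10% fall | 47-70% |
| 15% benefit | none | 82-96% |
| 15% benefit | 5% rise | 53-76% |
| 15% benefit | 10% rise | 23-36% |

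**5. Simulation checks.**

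- Counts with period labels permuted within community (r = 0.0225, f = 0.95, persistent CV 0.34, kw = 0): rejection of 4%, 12%, 21% and 65% for falls of 0, 3, 5 and 10%. The matching run with kw = 0.34 was not fully exchangeable (7% at no fall) and is not relied on, so the low ends in the table rest on the normal formula.
- A cluster-robust Wald test on the contingency SAP's inputs (6,000 trials per setting, kw = 0, 2% / 2.5% mortality): 18% / 21% for a 5% fall and 56% / 65% for a 10% fall. A 15% calendar fall with no drug effect (89% / 95%) looks almost the same as a true 15% drug effect with no trend (90% / 95%).

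**6. Arm-by-period interaction.** A proportional change shared by both arms cancels. In the second simulation it rejected in 4.7-5.5% of trials with no drug effect under common falls of 0-15%. For effect e its SE = sqrt(1/D1 + 1/[PY r(1-e)] + 1/[D1(1-e)] + 1/[PY r(1-e)] + 4kw^2/311), about 1.43 times that of item 3. Power is 52-74% for a 15% effect and 77-94% for 20%.

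It has two limits:

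- It assumes a stable effect in the continuing arm. If that effect moves from 15% to 7.5%, the expected ratio is 0.85/(0.925/0.85) = 0.78; if it moves to 20%, 0.85/(0.80/0.85) = 0.90. Neither is 0.85.
- Study A runs only after evidence of benefit in Stage 1, so there is regression to the mean. With no trend and no drug effect, an illustrative gate of Niger z < -1.96 gives rejection of 12-26% for the interaction and 8-15% for item 3. At z < -1 the figures are 7-11% and 6-8%.

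**The case against.** The strongest reply is that the SAP calls item 3 a longitudinal comparison and never a test of drug effect. A P-value for change between periods is valid for that question, so the harm needs a misreading. That is fair as far as it goes. But item 3 defines its periods by treatment received and carries no caveat, so the misreading is easy.

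Much of what is needed is also already planned: the Study A between-arm ratio, the Niger-only Stage 1 analysis (SAP 2.1.1, secondary 8), Stage 1 analyses by period and year (secondaries 2 and 4), and the slope in item 4d. This stands, and it makes the fix cheap. None of these is tied to item 3, and a linear slope is not the 1-4 versus 5-6 ratio.

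The contingency SAP does promise to look for secular effects, but in its Morbidity Study paragraph, about a separate and much smaller set of communities (15 per arm). That paragraph has them still on placebo, while Design says all Niger communities are treated; those passages must be reconciled.

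Two further points stand as limits. Every error rate above depends on an assumed trend. And the real Stage 2 gate is the pooled three-country primary, not Niger alone. An approximate pooled gate (z < -1.96, Niger about 69% of deaths, Tanzania at its planning size of 600) gives about 10-19% for the interaction and 8-12% for item 3, so the strong-gate figures above are on the high side. The caveat and the side-by-side ratio are better supported than the formal interaction test, which has its own weaknesses.

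**Conclusion.** The concern holds, as a minor point. The confounding is certain: it follows from the simultaneous switch and the one-arm contrast, whatever the model or permutation scheme. Its practical size is not known, because the documents give no secular rate for Niger; the rejection rates show sensitivity to assumed changes, not expected error. A total fall of 5% would raise the chance of a spurious P<0.05 to roughly three to five times nominal.

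The scope is this one secondary analysis and the matching emphasis in item 4a. The Study A primary compares concurrent arms, the Study B comparison is rerandomized, and no trial-level decision is tied to item 3.

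**What to change.** 1. Keep item 3, but label the placebo-arm before-after ratio a non-randomized estimate that assumes no secular trend, and do not present its P-value as a test of drug effect. State which labels are permuted.
2. Report beside it the same intervals 1-4 versus 5-6 ratio for the original azithromycin arm.
3. Add a companion arm-by-period interaction: negative binomial regression on both original arms, with significance from permuting original arm labels across whole communities, both periods kept together.
4. Reword the last sentence of item 3 so that it refers to clustering only.
5. State the companion's limits: lower power than item 3; a stable effect assumed in the continuing arm, although Protocol Chapter 2 makes durability of the effect a study question; and a 5% error that is unconditional on the Stage 1 result, with a note on regression to the mean.

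The cost is SAP wording, one more reported ratio and one model term, with no new data. The interaction's point estimate is essentially the Study A log rate ratio minus the Stage 1 Niger one, both already planned, so only its formal test is new. It should accompany item 3 rather than replace it, because it has less power and, with no trend, is more sensitive to the Stage 1 gate.
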